3.5.1. Adverse Events of Special Interest

The TEAEs of special interests will be defined based on a list of MedDRA Preferred Terms provided by Pfizer Pharmacolvigillance. A final list will be provided to programming prior to database release.

3.5.2. Labs

Hematology and chemistry result will be programmatically graded according to the National Cancer Institute's (NCI) CTCAE version 4.03 for relevant parameters.

4. ANALYSIS SETS

Data for all subjects will be assessed to determine if participants meet the criteria for inclusion in each analysis population prior to unblinding and releasing the database and classifications will be documented per standard operating procedures.

4.1. Intent-to-Treat

The intent-to-treat (ITT) population is defined as all patients randomly assigned to study treatment. The ITT population (or a subset thereof) will be used for all efficacy analyses and PRO analyses unless otherwise specified, and will be analyzed based on randomized treatment assignment, regardless of whether or not study treatment was administered.

4.2. Safety Analysis Set

The safety analysis set will include all randomized patients who receive at least 1 dose of any study drug. Unless otherwise specified, all safety analyses will use the safety population according to the actual treatment received (not the treatment assigned).

4.3. Evaluable Intent-to-Treat (eITT) Set

The evaluable ITT (eITT) set is defined as all ITT patients who have confirmed nonmetastatic disease at baseline by independent central radiology review. The eITT population will be used for certain efficacy analyses.

5. GENERAL METHODOLOGY AND CONVENTIONS

5.1. Hypotheses and Decision Rules

5.1.1. Hypotheses and Sample Size Determination

The study is designed to test the following primary hypothesis:

$$H_{0l}: \frac{\lambda_{TrtA}}{\lambda_{TrtC}} = 1$$
, versus $H_{al}: \frac{\lambda_{TrtA}}{\lambda_{TrtC}} \neq 1$, where

Trt A: Enzalutamide plus leuprolide;

Trt C: Placebo plus leuprolide.

The sample size and event-driven readout was chosen to adequately power the testing of the primary endpoint of MFS.

The comparison of MFS for enzalutamide monotherapy versus placebo in combination with leuprolide is a key secondary endpoint.

The following assumptions were used in determining the sample size calculation for the MFS endpoint:

- Overall 2-sided Type I error rate: 0.05
- Patient accrual rate: An adaptive enrollment rate has been modified into 2 arms to fit into EAST v6.4 software from Cytel
- Randomization: 1:1:1
- Median MFS for the control group: 55 months

An observed 142 MFS events in the 2 blinded treatment groups will provide approximately 90% power to detect a target hazard ratio of 0.58 using a 2-sided log-rank test with a 0.05 level of significance. This target hazard ratio corresponds to a difference of approximately 40 months in median MFS assuming an exponential distribution for MFS and a constant hazard rate for each group. For the key secondary hypothesis of MFS for the monotherapy arm, the target effect size, and expected number of MFS events will be the same as the primary hypothesis in the combination arm. As a 2-sided alpha of 0.03 will be utilized for the monotherapy comparison, the power for this analysis will be 86% with 142 MFS events observed. At the time of the final analysis, at least 197 MFS events total are expected for the 3 treatment groups. The study will require approximately 1050 patients (350 in each group) to achieve the 197 MFS events across the 3 treatment arms. This sample

size calculation accounts for a 5% loss to follow-up by the end of 4 years for all 3 treatment groups.

An actual enrollment of 1068 patients will also allow for an assessment for the key secondary endpoint of OS.

The significance level associated with the test of OS, in blinded treatment arm and monotherapy arm comparisons, will depend on the outcome of the key secondary endpoints (see Figure 2). If all key secondary endpoints for the blinded treatment arms are statistically significant then an α of 0.02 will be contributed to the comparison of OS according to the gatekeeping procedure. Similarly, if all key secondary endpoints for the monotherapy treatment arm are statistically significant then an α of 0.03 will be contributed to the comparison of OS. With 191 deaths, the power to detect a hazard ratio of 0.67 is 79.0% (if all key secondary endpoints are significant for both the blinded arm and monotherapy arm comparisons), 72.3% (if the key secondary endpoints are significant for the monotherapy arm only) or 67.0% (if the key secondary endpoints are significant for the blinded arms only) using a 2-sided log-rank test at a significance level of 0.05, 0.03 or 0.02, respectively, and a 2-look group sequential design with a Haybittle-Peto efficacy boundary (Haybittle et al. 1971, Peto et al. 1976).

5.1.2. Decision Rules

There will be no interim analysis for the primary endpoint (MFS). The interim and final analyses for the key secondary endpoint OS will be performed after the target number of events have occurred in the 3 treatment arms. A maximum of 2 distinct analysis cut-offs are planned according to the numbers of events described below:

- Final MFS and OS interim analyses at the time when 197 MFS events have occurred for the 3 treatment groups;
- Final OS analysis at the time when 271 deaths have occurred for the 3 treatment groups.

Table 2 shows the efficacy boundary associated with the final analysis of the primary endpoint of MFS between enzalutamide plus leuprolide and placebo plus leuprolide, according to independent central radiology review.

Table 2. MFS Based on Independent Review (2 Blinded Treatment Arms) - Efficacy Boundary

Analysis	Analysis Cut-Off Trigger	Number of MFS Events (2 Blinded Arms) ^a	Fraction of Required MFS Events	p-value (z-value) for Efficacy
Final MFS	197 MFS events in 3 arms	142	100%	≤0.05 (-1.9600)

MFS = metastasis-free survival

^a Number of events expected for MFS in blinded treatment arms assuming a hazard ratio of 0.58.

Table 3 shows the analysis triggers for OS as well the associated Haybittle-Peto efficacy boundaries. The significance level for the analyses of this key secondary endpoint is determined by the gatekeeping procedure.

Analysis	Analysis Cut- Off Trigger	Number of OS Events (2 Blinded Arms) ^a	Fraction of Required OS Events	p-value (z-value) for Efficacy ^b
IA OS	197 MFS events in 3 arms	82	43%	≤0.0001 (-3.89059)
Final OS	271 OS events in 3 arms	191	100%	≤0.04999 (-1.96001)

 Table 3.
 OS (2 Blinded Treatment Arms) - Efficacy Boundaries

OS = overall survival; IA = interim analysis; MFS metastatic-free survival.

a. Number of events expected for OS in blinded treatment arms assuming a hazard ratio of 0.67.

b. The p-values and z-values noted for OS are those associated with the scenario where all the key secondary endpoints for the blinded treatment arms and the monotherapy arm are statistically significant (α =0.05).

At the time of final analysis for MFS, a statistically significant difference for MFS between the enzalutamide plus leuprolide and placebo plus leuprolide arms (in favor of enzalutamide plus leuprolide) would trigger subsequent analyses of the remainder of the endpoints in Figure 2, including the key secondary endpoint of OS.

At the time of the final analysis for MFS, OS data will not be mature. The final analysis of overall survival will be performed at the time of the specified target numbers of deaths have occurred for the 3 treatment groups in Table 3. Long-term follow-up data (survival status and skeletal related events and new prostate cancer therapies, and progression on first subsequent therapy) will be collected every 12 weeks until the final OS analysis.

Based on the planned testing procedure in Section 5.1.3 and the actual results from tests for the primary endpoint and key secondary endpoints at the time of final analysis for primary endpoint, the analysis of OS for the combination arm will be tested at the alpha level of 0.05. The analysis of OS for the monotherapy comparison will be tested hierarchically as planned at the same alpha level as the combination arm comparison if significant (Figure 2 and Table 3).

In the final OS analysis, the significance level will be adjusted for the interim OS analysis following the specified Haybittle-Peto efficacy boundaries (Table 3). The analysis of OS in the aforementioned final analyses will be based on an ITT approach.

At the time of final analysis of OS, updated results from following secondary endpoints including time to first use of new antineoplastic therapy, time to first symptomatic skeletal event and progression free survival on first subsequent therapy will be summarized

descriptively and provided as exploratory analysis. No other efficacy endpoints (only OS) will be formally tested.

5.1.3. Multiplicity Adjustment for Efficacy Analysis

Alpha protected efficacy analyses will include tests for the primary endpoint of MFS for enzalutamide plus leuprolide versus placebo plus leuprolide, and all 3 key secondary efficacy endpoints (time to PSA progression, time to first antineoplastic therapy, and overall survival) for the combination comparisons. Additionally MFS, time to PSA progression, time to first antineoplastic therapy, and overall survival will be tested for enzalutamide monotherapy versus placebo plus leuprolide.

If the test for the primary endpoint (MFS in the combination arms) is significant at the full 2-sided alpha level of 0.05, the key secondary endpoints for the combination arms will be tested at a 2-sided alpha of 0.02 utilizing a hierarchical approach to preserve the family-wise Type I error rate. The remaining 0.03 alpha will be allocated to compare MFS as well as other key secondary endpoints for enzalutamide monotherapy versus placebo plus leuprolide. The efficacy analyses and the multiplicity adjustment rules are summarized in Figure 2.

The details of the approach and testing flowchart are as follows:

Step 1. Test MFS for enzalutamide plus leuprolide versus placebo plus leuprolide: Compute 2-sided p-value for MFS. If and only if p-value <0.05, declare statistical significance for MFS for the enzalutamide plus leuprolide versus placebo plus leuprolide treatment arm, then go to step 2 and step 3 below (as illustrated in testing flowchart Figure 2, the testing path is split into two branches). Otherwise stop.

Step 2. Testing of the 2 key secondary endpoints for enzalutamide plus leuprolide versus placebo plus leuprolide: Allocate a 0.02 alpha for testing the 3 key secondary endpoints using a hierarchical approach to preserve the family-wise Type I error rate. Proceed as follows:

If time to PSA progression is significant at the 2-sided alpha level of 0.02, declare statistical significance for this endpoint. Then the alpha of 0.02 is carried forward to test for the next endpoint of the time to first use of antineoplastic therapy. Otherwise stop.

If the time to first use of antineoplastic therapy endpoint is significant at the 2-sided alpha level of 0.02, declare statistical significance for this endpoint, then the alpha is carried forward to test the third endpoint of overall survival. Otherwise stop.

Step 3. Test MFS for enzalutamide monotherapy versus placebo plus leuprolide: Compute the 2-sided p-value for MFS. If and only if p-value <0.03, declare statistical significance for MFS for this treatment arm, then go to step 4 below. Otherwise stop.

Step 4. Testing of the 2 key secondary endpoints for enzalutamide monotherapy versus placebo plus leuprolide:

If time to PSA progression is significant at the 2-sided alpha level of 0.03, declare statistical significance for this endpoint. Then the alpha of 0.03 is carried forward to test for the next endpoint of the time to first use of antineoplastic therapy. Otherwise stop.

If the time to first use of antineoplastic therapy endpoint is significant at the 2-sided alpha level of 0.03, declare statistical significance for this endpoint, then the alpha level is carried forward to test the third endpoint of overall survival. Otherwise stop.

Step 5. Testing of overall survival for enzalutamide plus leuprolide versus placebo plus leuprolide

If all key secondary comparisons for the combination arm comparisons are significant at the alpha level of 0.02, and for the monotherapy comparisons at the alpha level of 0.03, then OS for the combination arm will be tested at the alpha level of 0.05. Otherwise, only the alpha from the significant set of key secondary comparisons will be carried forward.

Testing of overall survival for enzalutamide monotherapy versus placebo plus leuprolide

• OS for the monotherapy comparison will be tested in a hierarchical fashion at the same alpha level as the combination arm comparison if significant.

All other efficacy analyses and associated p-values will be deemed exploratory, for which no adjustment for multiplicity will be made.

At the time of final analysis of OS, no other efficacy endpoints (only OS) will be formally tested.

Figure 2. Key Efficacy Analyses and Multiplicity Adjustment

* $\alpha_4 = \alpha_2 + \alpha_3 = 0.05$ if all Combo and Mono comparisons are significant = $\alpha_2 = 0.02$ if Combo comparisons are significant and Mono are not = $\alpha_3 = 0.03$ if Mono comparisons are significant and Combo are not

5.2. General Methods

5.2.1. Pooling of Centers

In order to provide overall estimates of treatment effects, data will be pooled across centers. The 'center' factor will not be considered in statistical models or for subgroup analyses due to the high number of participating centers in contrast to the anticipated small number of patients randomized at each center.

5.2.2. Presentation of Continuous and Qualitative Variables

Continuous variables will be summarized using descriptive statistics ie, number of nonmissing values and number of missing values [ie, n (missing)], mean, median, standard deviation (SD), minimum, maximum and first and third quartile (Q1 and Q3).

Qualitative variables will be summarized by frequency counts and percentages. Unless otherwise specified, the calculation of proportions will include the missing category. Therefore counts of missing observations will be included in the denominator and presented as a separate category.

In case the analysis refers only to certain visits, percentages will be based on the number of patients still present in the study at that visit, unless otherwise specified.

5.2.3. Date of Last Contact

The date of last contact will be derived for patients not known to have died at the data cutoff date using the latest complete date (ie, imputed dates will not be used in the derivation) among the following:

- All patient assessment dates (eg, laboratory blood draws), vital signs, physical exam, performance status, (tumor assessments);
- Start and stop dates of concomitant therapies including non-drug treatments or procedures;
- Completion dates for PRO Questionnaires;
- Start and end dates of antineoplastic therapies administered after study treatment discontinuation including systemic therapy, radiation, and surgeries;
- AE start and end dates;
- Last date of contact collected on the 'Survival Follow-up' Case Report Form (CRF) (do not use date of survival follow-up assessment unless status is 'alive');
- Study treatment start and end dates;
- Randomization date; and

• Date of discontinuation on disposition CRF pages (do not use if reason for discontinuation is lost to follow-up or death).

Only dates associated with actual examinations of the patient will be used in the derivation. Dates associated with a technical operation unrelated to patient status such as the date a blood sample was processed or dates data were entered into the CRF will not be used. Assessment dates after the data cutoff date will not be applied to derive the last contact date.

5.2.4. Adequate Tumor Assessment

For soft tissues assessments by BICR, no assessments of CR, PR, or stable disease will be made given that the patient population is non-metastatic at study entry. The assessment options will be no disease (ND), no progression (NN), progressive disease (PD), or not evaluable (NE).

For bone assessment by BICR the assessment options will be No Bone Metastases (NBM), Bone metastases - unconfirmed (BPDu), Bone metastases (BPD), or NE.

For analyses based on BICR, a tumor assessment is defined as adequate when both bone and soft tissue assessments are evaluable (there is no NE in either bone or soft tissue) and the difference between bone and soft assessments dates is less than 25 weeks (of note, radiographic assessments are at 24 week \pm 5 days intervals in study schedule of activities). If either bone or soft tissue assessment is NE, the assessment would be considered as "inadequate".

For analyses based on investigator assessments, a tumor assessment is defined as adequate if both a bone scan and a soft tissue assessment are performed and the difference between bone and soft assessments dates is less than 25 weeks.

However, an assessment indicating PD from either a bone scan or a soft tissue assessment will be considered as adequate for declaring PD for analyses based on BICR and investigator assessment.

5.2.5. Definitions and Computations

Study Day

The study day for assessments occurring on or after the first dose of study treatment (eg, adverse event onset, tumor measurement) will be calculated as:

Study day = Date of the assessment/event - start date of study treatment/randomization date + 1.

The study day for assessments occurring prior to the first dose of study treatment (eg, baseline characteristics, medical history) will be negative and calculated as:

Study day = Date of the assessment/event – start date of study treatment.

The study day will be displayed in all relevant data listings.

Treatment Duration

The following durations will be calculated (of note, the data cutoff date is considered in calculation when last dose date and antineoplastic therapy date are not available):

Treatment Duration = Date of last dose of study drug – Date of first dose of study drug + 1

Treatment Suspension Duration (only for patients who suspend due to undetectable PSA at week 36) = Last Date of suspension without drug (ie, First dose after suspension-1 or Date of data cutoff, whichever occurs first) -First date of suspension +1. Treatment Suspension Duration will be missing for patients who do no suspend treatment due to undetectable PSA at week 36.

Modified Treatment Duration = Treatment duration – Treatment Suspension Duration + 1 for patients who suspend due to undetectable PSA at week 36. The Modified Treatment Duration will equal the Treatment duration for patients who do not suspend treatment due to undetectable PSA at week 36.

Treatment Duration After Reinitiation (only for patients who suspend due to undetectable PSA at week 36 and subsequently reinitiate treatment) = Date of last dose of study drug – First dose after suspension + 1. Treatment Duration after Reinitiation will be missing for patients who do no suspend treatment due to undetectable PSA at week 36 as well as patients who suspend but do not reinitiate treatment.

Long-Term Follow-up Period

Long-term follow up begins after safety follow-up. Visits repeat every 12 weeks (\pm 7 days) based on the 12-week visit schedule determined at randomization.

PSA Doubling Time Calculation

Patients' PSA doubling time will be calculated by the sponsor prior to randomization. All PSA values used for calculation will be examined during randomization stage and captured on the CRF page. To calculate PSA doubling time:

- a. All PSA values used in the calculation should be ≥ 0.20 ng/ml and follow a rising trend;
- b. All PSA values obtained over a maximum period of 12 months should be included in the calculation;
- c. Minimum requirements for the calculation are 3 PSA values obtained over 3 months with a minimum of 4 weeks between measurements;
- d. PSA values from the same local laboratory are preferred;
- e. All PSAs should be obtained following primary treatment for prostate cancer.

PSA doubling time calculation will be performed by using the method of Pound et al (Pound, 1999). A linear regression model will be used with log-transformed PSA values as the response and the duration of time from the first reference PSA value as the explanatory

PFIZER CONFIDENTIAL

variable. The slope from the fitted regression line will be used to calculate PSA doubling time in months as follows:

PSA Doubling Time (months) =
$$\frac{\text{LN}(2)*12}{(365.25*\text{Slope})}$$
.

Of note, LN stands for natural logarithm function.

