3.4. Baseline Variables

3.4.1. Study Drug, Study Treatment, and Baseline Definitions

The date of first dose (start date) of study treatment in the combination arms is the earliest date of non-zero dosing for each of the study drugs (enzalutamide/placebo or leuprolide).

The date of first dose (start date) of study treatment in the enzalutamide monotherapy arm is the earliest date of non-zero dosing of enzalutamide.

The date of last dose of study treatment in the combination arms is the latest date of non-zero dosing for each of the study drugs.

The date of last dose of study treatment in the enzalutamide monotherapy arm is the latest date of non-zero dosing of enzalutamide.

Definition of Baseline:

No windowing will be applied when defining baseline. For example, the protocol requires safety assessments to be performed within 28 days prior to randomization; however, values outside this window will not be excluded when determining baseline assessments. Any deviations from the protocol specified window will be documented as protocol deviations.

Definition of baseline for efficacy and baseline analyses

The last measurement prior to randomization will serve as the baseline measurement for efficacy and baseline analyses.

Definition of baseline for PRO

Per protocol, the first PRO assessment is planned to occur prior to dosing on Day 1; therefore, the last measurement on or prior to the day of first dose of study treatment (on or prior to randomization for patients randomized but not dosed) will be used as the baseline measurement.

Definition of baseline for safety analyses

The last available assessment on or prior to the date of first dose of study treatment (or prior to randomization for patients randomized but not dosed) is defined as the 'baseline' value or 'baseline' assessment for safety analyses. If an assessment is planned to be performed prior to the first dose of study treatment in the protocol and the assessment is performed on the same day as the first dose of study treatment, it will be assumed that it was performed prior to study treatment administration, if assessment time is not collected or is missing. If assessment times are collected, the observed time point will be used to determine pre-dose on study Day 1 for baseline calculation (this only applies for safety). Unscheduled assessments will be used in the determination of baseline.

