3.5. Safety Endpoints

Safety will be assessed through adverse event (AE) reporting, laboratory and vital sign assessments. AEs will be graded by the investigator according to the Common Terminology Criteria for Adverse Events (CTCAE) version 4.03 and coded using the Medical Dictionary for Regulatory Activities (MedDRA) version in use at the time of database release.

Safety endpoints will be summarized based on the on-treatment period, modified treatment period, or re-initiation treatment period as specified.

On-Treatment Period

The on-treatment period is defined as the time from the date of first dose of study treatment through a minimum of 30 days after last dose of study treatment, or the start day of new antineoplastic drug therapy -1 day, where the last dose of study treatment is the final dose after any suspension period due to undetectable PSA. Adverse events occurring on the same day as the first dose of study treatment will be considered to have occurred during the on-treatment period. All other assessments which occur on the same day as the first dose of study treatment will be considered baseline assessments (see Section 3.5).

Safety data collected outside the on-treatment period as described above will be listed but not summarized.

Modified Treatment Period

For patients whose treatment is suspended due to undetectable PSA at week 36 the modified period is defined as the period of time of study drug exposure starting from the date of the first dose of study drug through 30 days after last dose prior to the treatment suspension PLUS the time period starting from date of first dose at study drug reinitiation through a minimum of 30 days after last dose of study treatment, or the start day of new antineoplastic drug therapy -1 day. If date of first dose at study drug reinitiation is earlier than 30 days after last dose prior to the treatment suspension, then the modified treatment period is the same as that on-treatment period.

For all other patients the modified treatment period is the same as the on-treatment period.

Reinitiation Treatment Period

The reinitiation treatment period is defined only for patients who suspend treatment due to undetectable PSA at week 36 and subsequently reinitiate treatment and is defined as the time

period starting from date of first dose at study drug reinitiation through minimum 30 days after last dose of study treatment, or start day of new antineoplastic drug therapy -1 day.

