5.3.1.1. Date of Last Dose of Study Treatment

No imputation will be done for first dose date. Date of last dose of study treatment, if unknown or partially unknown, will be imputed as follows:

• If the last date of study treatment is completely missing and there is no End of Treatment (EOT) CRF page and no death date, the patient should be considered to be ongoing and use the data cutoff date for the analysis as the last dosing date; or

• If the last date of study treatment is completely or partially missing and there is either an EOT CRF page or a death date available (on or prior to the data cutoff date), then impute this date as the last dose date:

= 31DECYYYY, if only Year is available and Year < Year of min (EOT date, death date),

= Last day of the month, if both Year and Month are available and Year = Year of min (EOT date, death date) and Month < the month of min (EOT date, death date), or

= min (EOT date, death date), for all other cases.

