6.7.4. Study Treatment Exposure

Data from patients in the safety population will be used to summarize exposure and compliance.

Enzalutamide

The summary of treatment exposure for enzalutamide will include the following information:

- Treatment duration (months)
- Treatment suspension duration (months)
- Modified treatment duration (months)
- Duration of treatment after reinitiation (months)
- Cumulative dose (mg)
- Average daily dose (mg/day).

Treatment duration, treatment suspension duration, modified treatment duration and duration of treatment after reinitiation (see Section 5.2.5) will be summarized both as a continuous measures and as categorical measures (≤ 6 months, 6 to <12 months, 12 to <24, 24 to <36, 36 to <48, 48 to <60, 60 to <72, and ≥ 72 where appropriate).

The cumulative dose is the sum of the actual dose levels that the patient received (ie, total dose administered).

Average daily dose is the cumulative dose divided by the modified treatment duration.

The total number of capsules taken and percent overall compliance will also be summarized. Number of capsules taken will be calculated based on the number of capsules dispensed at all study visits minus the number of capsules indicated as returned. The total cumulative dose in milligrams (mg) will be calculated as (40 mg \times number of capsules taken), as each capsule is equivalent to 40 mg of the study drug or placebo.

Percent overall compliance rate will be defined as the number of capsules taken during the study divided by the expected number of capsules, multiplied by 100. Capsules from bottles not returned will be subtracted from the number of capsules taken and the expected number of capsules in calculating percent overall compliance rate. Each patient will be taking 4 capsules each day while on study treatment. A patient's expected number of capsules will be calculated as $[4 \times (\text{date of last dose prior to data cutoff date – date of first dose of study drug + 1)]$. However, for patients who have dose modifications (eg, dose reduction or dose withholding, or drug suspension due to undetectable PSA), the expected number of capsules will be summarized both as a continuous measure and a categorical measure in increments of 20%.

A data listing will be provided to present dose administration, modifications, and the derived compliance variables.

Dose Reduction and Modification

A dose reduction is defined as a non-zero dose that is less than the prior dose.

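### SAP 5.2.5 subtracts suspension time running to data cutoff from a treatment duration that has already ended, so modified duration and average daily dose can be negative for patients who stop or die while suspended

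*SAP*

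**What the plan says.** SAP 5.2.5 builds three linked durations.

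- **Treatment Duration** is last dose minus first dose plus 1. SAP 3.4.1 states that the last-dose date in the combination arms "is the latest date of non-zero dosing for each of the study drugs"; the monotherapy arm uses the same rule for enzalutamide alone.
- **Treatment Suspension Duration** runs from the first date of suspension, which is not defined, to "First dose after suspension-1 or Date of data cutoff, whichever occurs first".
- **Modified Treatment Duration** is Treatment Duration minus "Treatment Suspension Duration + 1 for patients who suspend due to undetectable PSA at week 36".

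A note at the head of these definitions brings in the data cutoff when neither a last-dose date nor an antineoplastic therapy date is available. SAP 5.3.1.1 covers missing last-dose dates. If the date is completely missing and there is neither an End of Treatment (EOT) page nor a death date, "the patient should be considered to be ongoing and use the data cutoff date for the analysis as the last dosing date". If an EOT page or death date exists, the imputed date is a month-end or year-end in some partial-date cases and otherwise "min (EOT date, death date), for all other cases".

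SAP 6.7.4 uses the result twice. "Average daily dose is the cumulative dose divided by the modified treatment duration", and the durations "will be summarized both as a continuous measures and as categorical measures", the lowest category being ≤ 6 months.

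**The concern.** The quantity subtracted is not contained in the quantity it is subtracted from. For a patient who restarts, suspension lies inside Treatment Duration and the subtraction makes sense. For a patient who leaves treatment while suspended, Treatment Duration ended before suspension began, yet suspension keeps accruing to data cutoff, past permanent discontinuation and even past death. Nothing caps suspension at those events or floors the result at zero.

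Such patients are expected. Protocol 5.4 gives a follow-up visit rule for those who permanently discontinue during suspension, and Protocol 10.4.1 provides for metastases and deaths occurring in that period.

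At stake are three exposure measures: suspension duration, modified duration and average daily dose. Protocol 10.6 asks for exposure over the time patients actually receive therapy, and for this group the SAP formula does not deliver it.

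**Working it through.** The documents give no duration figure to reproduce, so the formulas are evaluated directly.

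**Inputs**

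- First dose: day 1. Suspension start: day 253, the week 37 target day in SAP Table 4, (37 - 1) × 7 + 1.
- Daily dose: 160 mg (SAP 2.2). Dosing on every day from 1 to 252 is assumed, so the cumulative dose is 252 × 160 = 40,320 mg.
- L = last-dose day used; C = cutoff day.

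**Formula for a patient who never restarts**

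- Treatment Duration = L
- Suspension Duration = C - 253 + 1 = C - 252
- Modified Duration = L - (C - 252) + 1 = L + 253 - C

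This is negative once cutoff is more than 253 days after L.

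**Recorded last dose, L = 252.** Modified Duration = 505 - C; the correct value is 252 days and 160 mg/day.

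| Cutoff day | Modified duration (days) | Average daily dose (mg/day) |
|---|---|---|
| 505 | 0 | undefined |
| 730 | 252 - 478 + 1 = -225 | -179 |
| 1460 | 252 - 1208 + 1 = -955 | -42 |
| 2190 | 252 - 1938 + 1 = -1685 | -24 |

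Moving the suspension day across its ±5-day window (248 to 258) moves the zero point only to day 495 to 515.

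**Last dose imputed to EOT or death on day 1000 (SAP 5.3.1.1).** Modified Duration = 1253 - C, which is -207 at day 1460 and -937 at day 2190. Suspension Duration is 1208 and 1938 days, although suspension lasted 1000 - 253 + 1 = 748.

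**Still suspended at cutoff.** If L is set to C, the result is 253 days (252 if the first suspension date is taken as day 252). If the recorded last dose is used, it is again 505 - C. The SAP does not clearly say which applies.

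**Categories.** 6 × 30.4375 = 182.6 days, so 505 - C falls in ≤ 6 months from cutoff day 323 onward, negative values included. The patient was dosed for 252 / 30.4375 = 8.3 months.

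**Where the planned cutoff falls.** Protocol 3.4 puts the final MFS analysis at about 90 months. Reading the accrual table in Protocol 10.7 as monthly rates for all arms gives 889.9 patients by month 48. If the last rate continues, (1068 - 889.9) / 33.3 = 5.35 more months, so accrual ends near month 53.3. Cutoff then falls between (90 - 53.3) × 30.4375 ≈ day 1116 for the last patient and 90 × 30.4375 ≈ day 2739 for the first. With the recorded last dose the result is 505 - 1116 = -611 to 505 - 2739 = -2234 days. Reading the rates as two-arm rates lengthens the shortest follow-up and enlarges the error.

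**The trailing + 1.** Take a restart on day 853 and last dose on day 1500, so that 252 + 648 = 900 days were dosed. If the first suspension date is day 253, the formula gives 1500 - 600 + 1 = 901. If it is day 252, it gives 1500 - 601 + 1 = 900. The + 1 is right or one day over (1/252, about 0.4%, at most) depending on the undefined date.

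**The case against.** The strongest textual argument is the note at the head of the SAP 5.2.5 durations. It can be read as making cutoff a fallback for patients without a last-dose or antineoplastic therapy date, so that a discontinued patient with a recorded last dose would not be carried to cutoff. But the suspension line itself names only restart and cutoff, and the note supplies no other end date. Even if suspension is ended the day before new antineoplastic therapy, the result is negative when that therapy starts after day 506, and patients who never receive such therapy gain nothing.

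Second, at the planned cutoff every recorded-last-dose case is strongly negative, and SAP 5.2.2 reports the minimum, so the continuous table would expose the fault. That is largely true. It does not cover the categorical table, where a negative value sits unremarked in ≤ 6 months. Nor does it cover imputed last-dose dates with cutoff up to 252 days later: death on day 900 and cutoff on day 1100 gives a plausible-looking 1153 - 1100 = 53 days. Spotting the fault would also leave the correction unspecified.

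Third, scope is narrow. Leuprolide is summarized by injections, compliance has its own provision for suspension, and restarters are right to within a day. This stands.

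Fourth, the protocol says the primary analysis is complete, and SAP 6.8 does not name exposure among the evaluations after amendment 5. This also stands. However, the formula remains in the current SAP with the final OS analysis still to come, and a later cutoff would enlarge the error if exposure is summarized again.

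**Conclusion.** The concern holds. As written, SAP 5.2.5 yields impossible values for patients who suspend and then discontinue or die without restarting, and no other SAP convention corrects this. With the recorded last dose, a negative value is the expected result for such a patient at the planned cutoff: about -611 to -2234 days where 252 is correct.

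These figures assume daily dosing at 160 mg through day 252, suspension on the week 37 target day, and the reading of the accrual table stated above. The sign does not depend on fine detail, since the shortest planned follow-up is more than twice day 505. With an imputed last dose, the result is negative only if cutoff is more than 253 days after the imputed date.

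The consequence is limited to the enzalutamide and placebo exposure tables in SAP 6.7.4. It should be corrected, but it does not bear on MFS, OS or adverse-event attribution. The + 1 is a side issue of at most one day.

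**What to change.** Amend SAP 5.2.5 as follows.

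1. Define Modified Treatment Duration as the sum of dosed segments: (last dose before suspension - first dose + 1), plus (last dose - first dose after suspension + 1) if treatment was restarted, otherwise 0. SAP 3.5 already builds the modified treatment period this way, with a first segment "PLUS the time period starting from date of first dose at study drug reinitiation". The worked patient then has 252 days and 160 mg/day at every cutoff, and the restarter has 900 days.
2. Define the first date of suspension as the day after the last pre-suspension dose.
3. End Treatment Suspension Duration at the earliest of the day before restart, permanent discontinuation (the EOT date), death or data cutoff.
4. State which last-dose date applies to patients still suspended at cutoff.

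The cost is a few lines of SAP text and a derivation update, with no new data. If exposure tables from the completed MFS analysis were produced with the formula as written, modified duration, suspension duration and average daily dose should be rerun.
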